### 6.2.2.2 MyEmbrace

MyEmbrace is a secure web portal used to configure an Empatica account for patients. The MyEmbrace includes profile configuration and user guides. There is no user-data visualization in the MyEmbrace portal.

The study coordinator will configure the Embrace watch and paired phone on behalf of the patient and/or parent/caregiver. Custom documentation is to be prepared so patients and their parents/caregiver need not be exposed to the MyEmbrace interface at any time.

### 6.2.3 Usability of the Empatica Embrace Watch System (Embrace)

In the context of investigational use, the experimental seizure detection and alert components can be activated for patients and caregivers with their informed consent about the experimental nature of the functionality. Usability testing to support patient home-use has been underway since March 2016 with eight iterations introduced prior to August 2016 (revision history on hand as per the Embrace Change-log). In-app getting started guides, quick-start documentation and troubleshooting guides are sufficient to support the vast majority of patient caregiver groups in current trials. Due to the fact that patients/caregivers will be enrolled by study staff, those who might otherwise be unable to get set-up independently should be able to be enrolled and on-boarded without issue. The Empatica Alert app Onboarding screens are shown in Figure 3, and also provided in [Appendix 3](#).

Figure 3: Empatica Alert App Onboarding Screens

### 6.2.4 Device Risks

The Embrace watch system is currently marketed in the United States for consumer use in sleep and activity tracking without the seizure detection and alerting components. It does not currently have FDA 510(k) clearance but was designed in compliance with IEC

60601-1-2:2014 standards. Empatica, the maker of the Embrace system, is a medical device company in compliance with EN ISO 13485 standards (cert No. 9124.EPTC).

### **6.3 BLINDING**

This is an open-label sub-study to OLE Study ZX008-5103.

## **7. SAFETY INSTRUCTIONS AND GUIDANCE**

The Embrace is similar to other smartwatches that have been worn by patients over multiple days, and is believed to present minimal risk. The device passes a small current across the skin surface (similar to capacitive sensors in nature). It is non-invasive composed of well-established materials used in wearable devices and designed with ISO 10993-5 standards. The only notable risk so far has been that some wearers of similar devices occasionally develop contact dermatitis. Risk of contact dermatitis has been mitigated by restricting the use of common allergens – including nickel and cobalt, which affect 11.8% and 2.3% of the population, respectively (Mortz, et al 2013) – in the device materials and selecting grades of stainless steel that have nickel levels well below those required by EU REACH regulations. Occasionally skin reactions in similar devices may be caused by bacterial build-up on a watch or watch band as opposed to the material of the device itself so users will be reminded to clean the devices regularly.

To date, there have been two reports of allergic reaction related to wearing the Embrace watch.

**Subjects will be instructed to use the sensor only on the surface of healthy skin, to clean the sensor regularly, and to stop wearing it if the skin becomes red, itchy, or broken in any way.**

The Embrace system does not transmit radio signals that may interfere with hospital equipment or life-sustaining medical equipment. While the device has the capability of wireless transmission, it uses the Bluetooth standard, which is a reserved 2.4 GHz frequency band used in consumer electronics and within transmission power requirements. The device is compliant with IEC 60601-1-2:2014, EN 300 301 328 489 standards on electromagnetic emissions and interference. The rechargeable LiPol battery has an integrated protection circuit and the power system meets IEC 62133 standards.

Any unanticipated adverse device events (regardless of seriousness or severity) and unanticipated problems related to study participation should be reported as in the main Study ZX008-1503.

The physiological signals recorded using this device will not be used to make diagnostic or treatment decisions.

Safety monitoring will be done as per the main Study ZX008-1503 protocol.

## **8. STATISTICS**

### **8.1 SAMPLE SIZE**

This sub-study is designed as a pilot exploratory study to provide preliminary information on the ease of use of the Embrace watch to detect seizures in outpatients with Dravet syndrome, therefore, the sample size is based on feasibility.

### **8.2 ANALYSIS POPULATIONS**

#### **8.2.1 Safety (SAF) Population**

Participants in the sub-study will be included in the main Study 1503 safety analyses, which will be performed on the SAF Population defined as all subjects who receive at least one dose of ZX008 during the open label extension.

#### **8.2.2 Embrace Treatment (EmB) Population**

The EmB Population for the sub-study is defined as all subjects who receive at least one dose of ZX008 and have valid Embrace seizure data for at least one week during the open label extension. Effectiveness analyses for the sub-study will be performed on the EmB Population.

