## **2. STUDY OBJECTIVES AND ENDPOINTS**

### **2.1 PRIMARY OBJECTIVE**

The primary objective of the study is:

- To assess the overall usability and performance (correct use and ease of use) of the Empatica Embrace Seizure Detection watch system (Embrace) in outpatients with Dravet syndrome.

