**Table 1: Schedule of Additional Assessments for Subjects Enrolled in the Sub-study**

Study Assessments	Visit 1 a	OLE Treatment Period			
		Visit 2		Visits 3-4 (Months 1-2) b	Visit 5 (EOS/ET) Month 12 c
Study Day	1 a	15		30, 60	90
		Clinic	Phone		
Informed Consent	X				
Entry Criteria	X				
Issue/fit Embrace watch system and provide instructions on its use	X				
Perceived Stress Scale (PSS)	X			X	X
Ease of Use Questionnaire		X		X	X
EQ-5D-5L (QoL of parent/caregiver)	X			X	X
HADS (Affect of parent/caregiver)	X			X	X

Abbreviations: EOS/ET=End of Study/Early Termination; HADS=Hospital Anxiety and Depression Scale; OLE=open-label extension; PSS=Perceived Stress Scale; QoL=Quality of Life

Note: All other Study ZX008-1503 procedures must be completed as described in the main study protocol.

a Visit 1/Day 1 for sub-study ZX008-1503-SS01 corresponds to Visit 1/Day 1 for the main Study ZX008-1503.

b Subjects who continue for an additional 3 months will repeat Study Day 30 and 60 procedures on Study Days 90 and 120, and the end of study visit will be Study Day 150.

c At EOS/ET, subjects will be required to return the Embrace watch and study iPod.

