### 3.3 STUDY DURATION

The duration of the main Study ZX008-1503 for an individual who enters from Study ZX008-1501 or ZX008-1504 Cohort 2 is up to approximately 54 weeks. All subjects will receive ZX008 for up to approximately 52 weeks in Study ZX008-1503 and all subjects, including those who prematurely discontinue from the study, will undergo an up to 2-week taper of study medication, at the conclusion of the study. Subjects will be permitted to participate in the sub-study for the initial 12 weeks of participation in the main OLE study (ZX008-1503). Subjects may have the opportunity to extend participation in the sub-study for up to 24 weeks.

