#### **8.3.2 Efficacy Analysis**

The primary criteria for evaluation in the sub-study is the change over time in the 5-point Likert Ease of Use Questionnaire to measure user experience.

Secondary exploratory efficacy criteria for evaluation include change over time in the following:

- Perceived Stress Scale (PSS) to measure caregiver burden.
- Correlation of monthly (28-day) convulsive seizure count between the Embrace watch and seizure diary.
- Size of EDA response during and in the post-ictal hour of convulsive seizures.
- Skin-surface temperature (measured on wrist).
- Frequency of fever-related convulsive seizures.
- Comparison of convulsive seizure count during periods of sleep, and during the combined titration and maintenance periods between the Embrace watch and seizure diary.
- Correlation of convulsive seizure time and classification as determined by Embrace watch and seizure diary.
- EQ-5D-5L to measure quality of life of the parent/caregiver quality of life while using the Embrace.
- HADS to measure affective symptoms of the parent/caregiver while using the Embrace.

All other efficacy criteria are identical to those in the main Study ZX008-1503.

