#### **8.4 STATISTICAL METHODS**

All safety data will be summarized as described in the main Study ZX008-1503 protocol and associated Statistical Analysis Plan. Efficacy analyses for sub-study participants that rely on the ERT seizure diary or are specific to the Embrace will not be included in the main Study ZX008-1503 analyses. Exploratory data for the Embrace watch system data will be processed as follows:

Continuous data will be summarized using descriptive statistics including means, standard deviations, medians, lower and upper quartiles, and ranges. Categorical variables will be summarized with frequencies and percentages. Confidence intervals will be calculated for key parameters or estimates as warranted.

A complete description of the statistical analyses and methods will be available in the Statistical Analysis Plan, which will be finalized before the database is locked.

The primary analysis will rely on descriptive statistics to summarize responses to the Ease of Use Questionnaire from each time point where the questionnaire is administered. In particular, the modal, ie, most frequent, response to each item on the questionnaire will be reported at each time point. Responses across all items on the questionnaire will be summed to create an overall index that will also be reported at each time point.

Exploratory data for the Embrace watch system data will be processed as follows:

- Embrace’s automated convulsive seizure detection results will be manually compared to the diary counts of convulsive seizures. Spearman rank correlation will be used to quantify agreement.
- The Spearman rank correlation described above will be repeated separately for events during periods of sleep and for events while awake, based on Embrace’s determination of sleep/wake (periods of sleep will be based on actigraphy and EDA as measured by the Embrace watch).

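### The primary Ease of Use summary names no analysis set, and the default (EmB) would drop users who never reach a week of valid Embrace data

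*Combined protocol and SAP*

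**What the plan says.** Section 8.2 defines two populations. The Safety Population (8.2.1) serves the main-study safety analyses. The EmB Population (8.2.2) requires a dose of ZX008 and that subjects "have valid Embrace seizure data for at least one week during the open label extension". The same section adds, without exception: "Effectiveness analyses for the sub-study will be performed on the EmB Population".

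Section 8.3.2, headed Efficacy Analysis, gives the primary criterion as "the change over time in the 5-point Likert Ease of Use Questionnaire to measure user experience". Section 8.4 says the primary analysis will use "descriptive statistics to summarize responses to the Ease of Use Questionnaire from each time point where the questionnaire is administered", in particular the most frequent response to each item and a summed index. It names no population, and adds: "A complete description of the statistical analyses and methods will be available in the Statistical Analysis Plan". That separate plan is not among the documents supplied.

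The primary objective (Section 2.1) opens "To assess the overall usability and performance (correct use and ease of use"), so correct use is part of what is being assessed.

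The questionnaire follows the visit schedule and has no data-validity condition. Table 1 places it at Days 15, 30 and 60 and in a last column labelled "Visit 5 (EOS/ET) Month 12", which covers both end of study and early termination.

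**The concern.** A minimum of one valid week makes sense for the seizure, electrodermal activity (EDA) and temperature analyses, which cannot be done without a signal. The questionnaire needs no signal. Under Section 4.1, capturing data relies on the family wearing the watch, keeping it near the paired iPod and charging it daily. Failure to obtain a valid week can therefore itself be a sign of poor usability. Filtering the usability result on that condition selects subjects partly on something close to the outcome.

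At stake is whether the headline ease-of-use result describes everyone given the watch or only those for whom it worked well enough to yield data. The supplied text plans no count of fitted subjects outside EmB. Section 8.3.1 analyses watch-related adverse events separately and Section 4.4 records reasons for discontinuation, but neither is tied to the usability denominator.

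**Working it through.** The plan has no figure to reproduce: up to 20 subjects is a feasibility number (Sections 3.2 and 8.1). The check has a textual part and an illustration.

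**Which set applies**

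- Section 8.2.2 sends effectiveness analyses to EmB.
- Section 8.3.2 lists Ease of Use under efficacy.
- Section 8.2.1 reserves the other population for safety.
- Section 8.4 selects time points, not subjects.
- Section 4.4 treats data from subjects who discontinue like those of completers. A completer without a valid week is also outside EmB, so this does not override the entry rule.

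EmB is therefore the only defined set available.

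**Who could have a form yet fall outside EmB**

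- Subjects who keep using the watch but never reach a valid week.
- Early stoppers who return a form at termination.

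Subjects with early trouble who later obtain one valid week stay in. The week may fall at any time in the extension, and subjects may "extend participation in the sub-study for up to 24 weeks".

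**Size, under assumptions**

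Let 20 subjects be fitted, k of them outside EmB, and m of those k have a form at the time point. All EmB subjects have a form. Those m rate g = 1 to 3 points harder than the EmB mean. Stating the gap as harder avoids the conflict over scale direction between Section 3.1 (1 is very easy) and Appendix 1 (5 is very easy).

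Shift in an item mean = m × g / (20 − k + m).

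| k | m | g = 1 | g = 3 |
|---|---|---|---|
| 1 | 1 | 1/20 = 0.05 | 3/20 = 0.15 |
| 2 | 2 | 2/20 = 0.10 | 6/20 = 0.30 |
| 2 | 1 | 1/19 = 0.05 | 3/19 = 0.16 |
| any | 0 | 0 | 0 |

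If g = 0 the shift is also zero. On the Appendix 1 coding, g = 3 needs an EmB mean of at least 4, since 4 − 3 = 1 is the bottom of the scale.

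*Summed index*, same gap on each item: with two items (Mate App item dropped, as Appendix 3 records the removal of that app), 0.10 to 0.30 for k = m = 1 and 0.20 to 0.60 for k = m = 2. With all three Appendix 1 items, 0.15 to 0.45 and 0.30 to 0.90.

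*Mode*, k = m = 2, so 18 in EmB: if 11 share a category, the largest possible rival is 7 + 2 = 9 and the mode holds. If 10 share it, a tie at 8 + 2 = 10 is possible.

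*Change over time*: a subject with one form contributes no within-subject change.

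*Chance that anyone is excluded*: the documents give no rate. If each of 20 subjects independently has probability p of never reaching a valid week, the chance of at least one exclusion is 1 − (1 − p)^20: 0.64 for p = 5%, 0.88 for 10% and 0.99 for 20%.

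**The case against.** The strongest reply is that no such exclusion is stated. Section 8.2.2 speaks of effectiveness and Section 8.3.2 of efficacy, Section 8.4 describes the primary summary without a population, and the SAP may name one. This stands as a limit on certainty. It does not supply another set, and nothing suggests the two words are meant to differ.

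Second, every Appendix 1 item asks about the last week. An early stopper who no longer wears the watch may have no use to rate, so a minimum exposure has some logic. This stands, and the fix must allow for it. It does not justify dropping people who did use the watch but whose data never qualified.

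Third, that group may be empty. One week at any time over 12 to 24 weeks may be a low bar, and Section 4.4 implies that some lost or damaged devices are replaced. This also stands, although the number cannot be anticipated while valid is undefined.

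Fourth, the direction of bias is plausible but not shown. A valid week can be missed through poor connectivity or enforced withdrawal with the main study, and the questionnaire measures perceived ease, not correct use.

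Finally, this is a descriptive pilot with no test or success threshold, which limits the consequence.

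A reader might infer that the protocol expressly removes everyone who had difficulty with the device, or that the usability result is known to be inflated. The documents support neither: the assignment is inferred, early difficulty followed by one valid week keeps a subject in, and no exclusion rate is given.

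**Conclusion.** The point holds as an inference from the supplied text, at low to moderate severity. As written, a usability result would by default be conditioned on having captured a valid week of device data, which plausibly favours the device.

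The item-mean range of about 0.05 to 0.30 rests on 20 fitted subjects, one or two excluded who have forms, and ratings 1 to 3 points harder than the EmB mean. The true effect is zero if nobody is excluded, if the excluded have no forms, or if they rate as the others do. The case for acting is that the choice affects the primary summary and is easy to settle before database lock.

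**What to change.** Add to Section 8.2: *Ease of Use will be summarised in all sub-study subjects fitted with an Embrace watch who have at least one questionnaire; the EmB summary is supportive.* In addition:

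- Flag forms completed when the watch was not used in the preceding week, and show the summary with and without them. Do not infer non-use from missing valid data alone, since that would bring the same filter back.
- Keep EmB for the seizure, EDA and temperature analyses.
- For the other caregiver forms (PSS, EQ-5D-5L, HADS), which Section 8.3.2 lists under the same heading, likewise use fitted subjects with a form.
- Report the number and percent of fitted subjects outside EmB, with reasons.
- Define valid data, including whether the week must be consecutive or may be cumulative.

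If the SAP already covers these points, a cross-reference is enough.

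The cost is a few lines of wording, one extra table and a source for the non-use flag, with no new visits or scales. The ease-of-use result may be less favourable, and little may be recovered if early stoppers return no form.

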### **8.3 DATA ANALYSIS**

#### **8.3.1 Safety Analysis**

Safety criteria will be identical to that in the main study ZX008-1503, and include AEs, laboratory safety parameters (hematology, chemistry, and urinalysis), vital signs (blood pressure, heart rate, temperature, and respiratory rate), physical examination, neurological examination, 12-lead electrocardiograms (ECGs), Doppler ECHOs, and body weight. The BRIEF will be administered to track cognitive function. Adverse events considered to be related to the Embrace watch will be analyzed separately for participants in the sub-study.

#### **8.3.2 Efficacy Analysis**

The primary criteria for evaluation in the sub-study is the change over time in the 5-point Likert Ease of Use Questionnaire to measure user experience.

Secondary exploratory efficacy criteria for evaluation include change over time in the following:

- Perceived Stress Scale (PSS) to measure caregiver burden.
- Correlation of monthly (28-day) convulsive seizure count between the Embrace watch and seizure diary.
- Size of EDA response during and in the post-ictal hour of convulsive seizures.
- Skin-surface temperature (measured on wrist).
- Frequency of fever-related convulsive seizures.
- Comparison of convulsive seizure count during periods of sleep, and during the combined titration and maintenance periods between the Embrace watch and seizure diary.
- Correlation of convulsive seizure time and classification as determined by Embrace watch and seizure diary.
- EQ-5D-5L to measure quality of life of the parent/caregiver quality of life while using the Embrace.
- HADS to measure affective symptoms of the parent/caregiver while using the Embrace.

All other efficacy criteria are identical to those in the main Study ZX008-1503.

#### **8.4 STATISTICAL METHODS**

All safety data will be summarized as described in the main Study ZX008-1503 protocol and associated Statistical Analysis Plan. Efficacy analyses for sub-study participants that rely on the ERT seizure diary or are specific to the Embrace will not be included in the main Study ZX008-1503 analyses. Exploratory data for the Embrace watch system data will be processed as follows:

Continuous data will be summarized using descriptive statistics including means, standard deviations, medians, lower and upper quartiles, and ranges. Categorical variables will be summarized with frequencies and percentages. Confidence intervals will be calculated for key parameters or estimates as warranted.

A complete description of the statistical analyses and methods will be available in the Statistical Analysis Plan, which will be finalized before the database is locked.

The primary analysis will rely on descriptive statistics to summarize responses to the Ease of Use Questionnaire from each time point where the questionnaire is administered. In particular, the modal, ie, most frequent, response to each item on the questionnaire will be reported at each time point. Responses across all items on the questionnaire will be summed to create an overall index that will also be reported at each time point.

Exploratory data for the Embrace watch system data will be processed as follows:

- Embrace’s automated convulsive seizure detection results will be manually compared to the diary counts of convulsive seizures. Spearman rank correlation will be used to quantify agreement.
- The Spearman rank correlation described above will be repeated separately for events during periods of sleep and for events while awake, based on Embrace’s determination of sleep/wake (periods of sleep will be based on actigraphy and EDA as measured by the Embrace watch).
- For each seizure, the peri-ictal EDA recording will be segmented from 60 minutes before detected seizure onset to 120 minutes afterward. A “significant EDA response” is declared when an increase in skin conductance level of more than 2 times the standard deviation of the pre-ictal baseline occurs. The time of the beginning of such an EDA response is defined as “EDA\_start,” the time of the maximum peak of the EDA response is defined as “EDA\_peak,” and the point in time following this peak, when the EDA falls below 10% of the peak amplitude is defined as “EDA\_end.” Significant EDA responses will be analyzed in terms of the amplitude of their EDA\_peak, the response duration, defined as the difference between “EDA\_end” and “EDA\_start,” and the natural logarithm of the area under the curve (AUC) of the rising phase (from “EDA\_start” to “EDA\_peak”) and of the total response (from “EDA\_start” to “EDA\_end”), ie, LogAUCrise and LogAUCtot. These measures will be examined to see if they vary over time with the treatment. Each of the measures will be evaluated for changes over time using a mixed model repeated measures (MMRE) that allows for a different intercepts for each subject (ie, a random effect) but a common slope over time (ie, a fixed effect).
- Skin-surface temperature changes will be averaged daily and compared over time, with separate comparisons made for “seizure-free” periods and for “pre-seizure periods.” The duration of these periods will be based on average 60-minute intervals, but may also be examined more with shorter intervals. Changes in skin-surface temperature over time will be evaluated using similar MMREs as described above for EDA endpoints.

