### 3.2 NUMBER OF SUBJECTS

Up to 20 subjects from the main Study ZX008-1503 will have the option to participate in sub-study ZX008-1503-SS01 upon separate consent and fulfillment of entry criteria as detailed in Sections 4.1 and 4.2. Subjects will be approached sequentially until the target number of participants is reached.

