#### **4.6 REPLACEMENT OF SUBJECTS**

Enrolled subjects will not be replaced.

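### The item-level summary singled out for the primary analysis is the mode, which is unstable with 20 or fewer respondents unless one category dominates, and cannot by itself show change over time

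*Combined protocol and SAP*

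**What the plan says.** Section 8.3.2 sets the target: "The primary criteria for evaluation in the sub-study is the change over time in the 5-point Likert Ease of Use Questionnaire". The synopsis says the same.

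Section 8.4 makes the primary analysis descriptive at each time point and then singles out one item-level statistic: "the modal, ie, most frequent, response to each item on the questionnaire will be reported at each time point". The next sentence adds a second named summary, the sum of all items as an overall index, also by time point. Earlier in the section, general rules give frequencies and percentages for categorical variables, the usual moments and quantiles for continuous ones, and confidence intervals where warranted. Fuller detail is left to a SAP to be finalised before database lock. Section 8.4 has no rule for a tied mode, no within-subject change summary for the questionnaire and no interval assigned to it.

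The numbers are small. Section 3.2: "Up to 20 subjects from the main Study ZX008-1503 will have the option to participate". Section 8.1: "therefore, the sample size is based on feasibility". Section 4.6: "Enrolled subjects will not be replaced". Section 8.2.2 limits effectiveness analyses to subjects who "have valid Embrace seizure data for at least one week during the open label extension", so fewer than 20 may contribute at a given visit.

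Appendix 1 has three five-category items: watch, Mate App and Alert App. Table 1 and section 5 place the first completion at Day 15.

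**The concern.** The mode records only which category has the most answers. It ignores the order of the scale and everything outside the largest cell. In a small sample one or two respondents can move it, and it may not be unique.

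The sub-study wants to know whether ease of use changes. A summary that can shift when nothing has changed, and hold still when much has, is a poor lead statistic for that. The primary analysis is wholly descriptive, so the choice of descriptor largely decides what the report will say about each item.

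**Working it through.** **Inputs.** n = 20 is the maximum (section 3.2); n = 15 and n = 10 stand for losses, since subjects are not replaced (section 4.6). Each item has five categories (Appendix 1). The response distribution is not in the documents, so it is assumed and varied. The plan states no precision or error figure for the mode, so there is none to reproduce.

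**1. How often the sample mode is tied or is not the true mode.** For counts c1 to c5 with probabilities p1 to p5,

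P(c) = n! / (c1! c2! c3! c4! c5!) × p1^c1 × p2^c2 × p3^c3 × p4^c4 × p5^c5.

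At n = 20 there are C(24,4) = 10,626 possible tables. Add P(c) over tables whose largest count is shared (tied), and over tables whose single largest count is not in the category with the largest p (wrong). Totals can differ by 0.1 from rounding.

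| Assumed % for scores 1 to 5 | Tied % | Wrong % | Total % |
|---|---|---|---|
| 2/3/5/70/20 | 0.4 | 0.3 | 0.7 |
| 2/5/8/60/25 | 2.0 | 2.8 | 4.9 |
| 5/5/15/50/25 | 4.9 | 7.7 | 12.6 |
| 5/10/15/45/25 | 7.0 | 11.8 | 18.9 |
| 5/10/20/40/25 | 10.7 | 20.0 | 30.6 |
| 5/10/20/35/30 | 13.5 | 36.7 | 50.2 |
| 10/20/25/30/15 | 17.4 | 39.1 | 56.6 |
| 5/15/25/30/25 | 17.1 | 44.4 | 61.6 |

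Losses make it worse: for 5/10/20/40/25 the total is 37% at n = 15 and 45% at n = 10.

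**2. Apparent change when there is none.** Simulate the same 20 people at two visits with one unchanged distribution, linking their answers through a latent normal variable (correlation assumed). At correlation 0.7 the modal category or set of tied categories differs between visits in about 57% of runs for 5/10/20/35/30, 45% for 5/10/20/40/25, 20% for 5/5/15/50/25 and 1% for 2/3/5/70/20. At correlation 0.9 the first of these is 48%.

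**3. Real change that the mode misses.** This needs no assumed distribution. Using the Appendix 1 coding (5 = Very easy):

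- Visit A, counts 0/1/3/9/7: mode 4 (Easy). Mean = (1×2 + 3×3 + 9×4 + 7×5)/20 = 82/20 = 4.10. Median 4. Easy or Very easy: (9 + 7)/20 = 80%.
- Visit B, counts 4/4/3/7/2: mode 4 (Easy). Mean = (4×1 + 4×2 + 3×3 + 7×4 + 2×5)/20 = 59/20 = 2.95. Median 3. Easy or Very easy: (7 + 2)/20 = 45%.

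The mode is unchanged while the mean falls by 1.15 points and the favourable share by 35 percentage points. Over all tables of 20 with a unique mode of 4, the mean can lie anywhere from 2.45 to 4.45, so a shift of up to 2.00 points can go unseen. Conversely, 0/0/1/10/9 to 0/0/1/9/10 moves the mode from 4 to 5 for a mean change of (89 − 88)/20 = 0.05.

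**4. Precision of the alternatives at n = 20.** The exact (Clopper-Pearson) limits for x of n are the 2.5% point of Beta(x, n − x + 1) and the 97.5% point of Beta(x + 1, n − x). For 16/20 they are 56% and 94%; for 13/20, 41% and 85%. For a mean paired change the 95% half-width is t(19) × SD/√20 = 2.093/4.472 × SD = 0.47 SD of the change.

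**The case against.** The strongest reply is that section 8.4 does not rest on the mode alone. The summed index is also a named primary summary. In the example above it would fall by 3 × 1.15 = 3.45 points if all three items moved alike. The general rule for categorical data would put the five frequencies in the tables, and the favourable share follows from them. This stands, and it limits the harm. It does not remove the point. The index cannot show which component changed, and it is not yet a clean fallback: section 3.1 codes 1 as very easy and 5 as very difficult, Appendix 1 codes them the other way round, and Appendix 1 still asks about the Mate App, which the amendment removed. No part of 8.4 specifies paired change for the questionnaire.

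Second, the error rates depend on the assumed distribution. That is right, which is why a range is shown. Where the top two categories are adjacent and nearly equal, reporting the other one is also a small error, such as Very easy for Easy.

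Third, this is an exploratory pilot sized on feasibility, with no test or success threshold, and the SAP can still settle tie handling and layout. Also right: no decision rule turns on the mode.

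Fourth, the share rating Easy or Very easy also discards information, and by visit it does not measure within-subject change. That is accepted, so the fix keeps the full distribution and adds paired change.

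**Conclusion.** The point holds as a matter of which summary the plan puts forward. The mode is the item-level statistic singled out for the primary analysis. At n of 20 or fewer it is unreliable unless one category clearly dominates, and it cannot alone describe change over time. Under the assumed distributions the tied-or-wrong rate at n = 20 runs from under 1% to about 62%. The masking example rests on no distributional assumption.

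Two stronger readings should be resisted. A reader might infer that the mode is wrong about half the time at this sample size. That figure belongs to one assumed pattern (35% and 30% in the top two categories); the documents give no distribution that would support it generally. A reader might also infer that a large change would go unreported. The summed index and the frequency tables would probably reveal much of it. The consequence is therefore moderate: a weak lead summary in a descriptive pilot, cheaply improved.

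**What to change.** In section 8.4 and the SAP:

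- Name as the primary item-level summary, at each time point, the full five-category distribution, the median, and the number and percentage rating Easy or Very easy with an exact 95% interval.
- Add the paired within-subject change from the first assessment (Day 15), with a 95% interval, for each item and for the summed index.
- Keep the mode only as a supplementary description, listing all tied categories when it is not unique.
- Before any index is interpreted, reconcile the scale direction between section 3.1 and Appendix 1, and settle the status of the Mate App item.

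The cost is a few sentences and a few extra table rows from data already collected. The intervals will be wide (13/20 gives 41% to 85%). Change measured from Day 15 says nothing about the first two weeks of use.
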